9.5 Handling of Multiplicity

If the primary efficacy variable is statistically significant, each of the key secondary variables will be tested using the fixed sequence in Section 9.3 as a gatekeeping procedure and at α level of 0.050. Testing will cease at the point that a secondary variable fails to demonstrate statistical significance.

9.6 Efficacy Subgroup Analysis

To determine if the following factors have an impact on the response to treatment, subgroup analyses will be conducted on the change from baseline to final visit on the UDysRS total score:

- Gender
- Age category ($< 65, \ge 65$)
- Duration of Parkinson's disease (< 10 years, \geq 10 years)
- Total daily dose of levodopa (< 1250 mg, ≥ 1250 mg) at the end of initial LCIG titration for the LCIG group and in the first set of dosing diary for the OMT group
- Number of anti-PD medications other than levodopa taken at any time during the week prior to randomization (0 or 1, 2 or more)

The subgroup analyses will be performed using an ANCOVA model contain treatment, country, and subgroup as main effects, treatment by subgroup interaction, and baseline score as the covariate. The LS mean change for each stratum of the subgroup with associated 95% confidence interval will be presented.

The descriptive statistic summary described for the UDysRS total scores will also be prepared for each subgroup stratum.

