from baseline to final = -1.8 [1.8], P = 0.014), increase in "On" time without troublesome dyskinesia (baseline = 7.4 [2.2], change = 4.4 [3.6], P = 0.004), and decrease in "Off" time (baseline = 5.5 [1.3], change = -2.7 [2.8], P = 0.015). Similar trends were found in the open-label study. An increase in levodopa-carbidopa intestinal gel dose was not significantly correlated with increased "On" time with troublesome dyskinesia in either study (double blind: r = -0.073, P = 0.842; open label: r = -0.001, P = 0.992). Adverse events were usually mild to moderate in severity and related to the gastrointestinal procedure.

When specifically evaluating the effect of LCIG treatment on dyskinesia in Parkinson's disease patients, no previous interventional studies have compared LCIG treatment to optimized medical treatment using the UDysRS as an endpoint.

UDysRS

The Unified Dyskinesia Rating Scale (UDysRS) is a rating tool specifically designed to assess dyskinesia in PD. It is composed of modified versions of previously existing rating scales and in a comprehensive way assesses both the subjective and the objective aspects of the presence of dyskinesia. Although relatively new, multiple clinical trials of new putative anti-dyskinesia agents are currently underway using UDysRS as the primary endpoint. The UDysRS contains both self-evaluation questions (completed by the patient alone or with their caregivers) and items that are assessed directly by the physician to objectively rate the abnormal movements associated with PD. The UDysRS contains four sections. Two sections examine the historical disability of ON-dyskinesia (Part 1) and OFF-dystonia (Part 2) as perceived by the patient. Two sections assess the objective impairment (Part 3) and disability (Part 4) caused by the dyskinesia during the time of assessment. All parts consist of several items and each item is scored on a scale from 0 – 4 in a Likert model (0 = normal to 4 = severe) and the total score can range from 0 - 104. Table 1 lists the sections and corresponding parts of the UDysRS.

Table 1. **UDysRS Sections**

Section	Part	Completed by	Measure	Number of Items	Score Range
Historical disability	Part 1	Patient/Caregiver	Patient perception of on-dyskinesia impact	11 items	0 – 44
	Part 2	Patient/Caregiver	Patient perception of off-dystonia impact	4 items	0 – 16

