Following optional NJ and/or PEG-J placement on Study Day 1 and, at the discretion of the Investigator, the subject may begin initiation and titration of LCIG infusion on Study Day 1 once tube placement is confirmed. All other oral anti-PD medications other than amantadine must be stopped prior to LCIG initiation. The dose of LCIG should be adjusted to obtain the optimal clinical response for the individual subject. Optimal clinical response, or optimization, is defined as maximizing the functional "On" time during the day and minimizing the number of "Off" episodes (bradykinesia) and the time the subject is "Off." In addition, optimization minimizes "On" time with troublesome dyskinesia. This determination is made by the Investigator. The dosage procedures for LCIG are described in Section 5.5.1 Treatments Administered.

Oral levodopa medication may only be used as a supplement during the night following discontinuation of the LCIG infusion. During the day it should be used ONLY as rescue medication in case of acute deterioration, presumably caused by failure of the tubes and/or the pump or the onset of an acute illness.

It may take several days to optimize LCIG treatment. In some subjects, optimization may take longer and if required, at the discretion of the investigator or local practitioner, subjects may be admitted and remain hospitalized for the duration of the titration period. For those subjects with an NJ placement they may or may not continue the NJ Period at home until the PEG-J is inserted.

During the initial titration phase, extra doses may be administered by the Investigator or subject every hour. Pump programming should only be done by trained site personnel and all dose changes must be approved by the Investigator. After the nightly discontinuation of LCIG drug administration, levodopa-DDI (DOPA decarboxylase inhibitor) tablets may be taken up to 2 hours (for oral LC-IR) or 4 hours (for oral LC-CR)

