The Maintenance Dose is adjustable in steps of 2 mg/hour (0.1 mL/hour). The dose should be calculated according to the subject's previous daily intake of levodopa. The continuous maintenance dose is adjusted individually. It is usually kept at 2 to 6 mL/hour (40 to 120 mg levodopa/hour). However, higher doses may be clinically indicated. During the titration period, the continuous dose can be titrated in a step wise fashion that meets the clinical and medical needs of the subject. The continuous maintenance dose is first calculated based on the subject's usual total daily dose minus the morning dose.

During treatment, pump alarms may indicate kinking or knotting of the tube. Additionally there may be a sudden deterioration in treatment response with recurring motor fluctuations due to the distal part of the tube becoming displaced from the upper intestine into the stomach. The location of the tube should be determined radiographically. If necessary, the end of the tube can be repositioned to the proximal small intestine and the new placement confirmed radiographically.

If a problem develops with the LCIG system and the LCIG infusion needs to be temporarily discontinued, the Investigator should then place the subject on a regimen of oral levodopa-IR tablets until the problem is resolved and the LCIG infusion can be resumed the following morning. If the subject is placed on an oral regimen of levodopa IR tablets; the dose prescribed should be based on the dose the subject was receiving just prior to the LCIG infusion interruption and adjust the dose as clinically indicated to stabilize the subject.

Extra LCIG Doses

During initial titration, extra doses may be administered on an hourly basis at the Investigator's discretion based on the subject's response. Subsequently, subjects will be allowed to self-administer additional extra doses of LCIG (at intervals of no less than 2 hours) to address immediate medical needs, such as the rapid deterioration of motor function. Extra doses may be given as required if the subject becomes hypokinetic during the day. If the need for extra doses exceeds 5 times per day, the subject should be instructed to contact the Investigator. The Investigator should then consider the need to increase the subject's continuous daily maintenance infusion dose. After the initial dose setting, fine adjustments of the morning dose, the maintenance dose and extra doses can be made as needed.

Nasojejunal Tube

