8.3 LCIG Daily Prescribed Dose

Each subject's LCIG dose will be individually titrated by adjustment of the LCIG pump settings for the morning dose (mL), continuous flow rate (mL/hr) and extra dose amount (mL). The initial LCIG pump settings and the LCIG pump settings at the conclusion of each clinic visit will be recorded on the Study Drug Prescription eCRF. Subjects are to administer LCIG over a full 16-hour period each day beginning with a morning dose. Extra doses are to be administered only if needed. The daily prescribed dose will be calculated as the morning dose plus 16 times the continuous flow rate. The daily

prescribed dose will be summarized in milligrams (mg) of levodopa using the conversion factor of 1 mL LCIG = 20 mg levodopa.

The daily prescribed dose will be summarized with descriptive statistics (number of subjects with non-missing observations, mean, standard deviation, median, minimum and maximum values) for the following.

- Initial LCIG prescription
- First optimized prescription following PEG-J placement
- Final prescription

Descriptive statistics will also be presented for the change in the daily prescribed dose from initial LCIG prescription to first optimized prescription following PEG-J placement and to final prescription and from first optimized prescription to final prescription.

8.4 **Total Daily Levodopa Dose**

For all randomized subjects, the total daily levodopa dose on the day prior to Visit 1 and on the day of randomization will be considered the subject's screening and baseline levodopa dose, respectively. Following Screening Visit 3, subjects randomized to the LCIG group will have NJ/PEG-J placement and discontinue all anti-PD medications other than levodopa-carbidopa that will be continued during LCIG treatment as post-infusion nighttime therapy. Subjects in the LCIG group are to record all LCIG infusions during the 3 days before each scheduled study visit on a Subject Dosing Diary. Subjects in the OMT group are to record all anti-parkinsonian medications taken on the Subject Dosing Diary.

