Duration of initial LCIG titration for each subject will be calculated as the date of the first optimized prescription minus the first LCIG infusion date + 1. The first LCIG infusion date will be recorded on the Study Drug Administration eCRF. The current

LCIG pump settings at the conclusion of each clinic visit will be recorded on the Study Drug Prescription eCRF. The first set of pump settings that remains unchanged for at least 7 days will be considered the first optimized prescription. The number and percentage of subjects with each specific number of titration days will be summarized. In addition, the duration of initial titration in days will be summarized with descriptive statistics (number of non-missing observations, mean, standard deviation, median, minimum and maximum duration).

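### The levodopa-dose subgroup is defined by a post-randomisation dose measured differently in each arm, so its treatment-by-subgroup term can show an interaction that is not there

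*SAP*

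**What the plan says.** SAP 9.6 lists five subgroup factors for the change from baseline to final visit in UDysRS total score. Each is fitted in an ANCOVA with treatment, country, subgroup, "treatment by subgroup interaction, and baseline score as the covariate", and the LS mean change with a 95% CI is reported per stratum.

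For levodopa dose (<1250 mg, ≥1250 mg) the value is taken "at the end of initial LCIG titration for the LCIG group and in the first set of dosing diary for the OMT group". The other four factors are fixed before treatment: gender, age, disease duration, and the number of other anti-PD drugs "taken at any time during the week prior to randomization".

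The related definitions are:

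- **LCIG dose.** Protocol 5.1.2.2 states: "The dose of LCIG should be adjusted to obtain the optimal clinical response for the individual subject". The aim is more functional ON time, fewer and shorter OFF episodes, and less ON time with troublesome dyskinesia. SAP 8.7 dates the end of initial titration: "The first set of pump settings that remains unchanged for at least 7 days will be considered the first optimized prescription".
- **OMT dose.** The Subject Dosing Diary is not marked at V3 in Protocol Table 4. For OMT patients it first appears at V5 (Week 2). Protocol 5.1.2.1 keeps the OMT regimen stable unless a change is medically indicated.
- **Baseline dose.** SAP 8.4 takes the total daily levodopa dose on the day before Visit 1 and on the day of randomisation as the "screening and baseline levodopa dose, respectively", for all randomised subjects.

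**The concern.** A treatment-by-subgroup term has a causal reading only if stratum membership is not influenced by treatment. Here it is. An LCIG patient's stratum depends on how the patient responded during titration, and on the levodopa needed after other anti-PD drugs were stopped. An OMT patient's stratum reflects a regimen that is meant not to change. LCIG patients at or above 1250 mg are therefore not the randomised counterparts of OMT patients at or above 1250 mg.

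The output would be read as showing whether the LCIG effect depends on levodopa requirement, when part of any difference could be produced by titration. There is also a gap in the definition. An LCIG patient who stops before pump settings have been unchanged for 7 days has no first optimised prescription under SAP 8.7, and so no clear stratum. The OMT arm has no equivalent loss.

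**Working it through.** **1. The plan's own figure.** SAP 4.3 gives no figure for the subgroup analysis, only the overall design: difference 10, SD 12, two-sided 0.050, 27 per group, 85% power. The noncentral t distribution with 27 per group gives 85.2%, and 27/0.9 = 30 per group, or 60 in total. Both reproduce. The effect of 10 and SD of 12 are used below.

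**2. Set-up.** The true effect is -10 in every patient, so the true interaction is zero. The following are assumptions, because the documents do not give them:

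- Baseline dose has mean 1150 mg and SD 400 mg.
- LCIG dose is baseline plus a titration change with mean 0 and SD 200 mg. OMT dose equals baseline.
- The titration change has correlation ρ with the patient's outcome.
- Baseline dose is not prognostic (relaxed in step 5).

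**3. Stratum effects.** The LCIG dose SD is √(400² + 200²) = 447 mg, so the correlation of the titrated dose with outcome is r = ρ × 200/447 = 0.447ρ. The standardised cut is c = (1250 − 1150)/447 = 0.224, with φ(c) = 0.389 and Φ(c) = 0.588.

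- Effect below the cut: −10 − 12r × φ/Φ = −10 − 12r × 0.661
- Effect at or above the cut: −10 + 12r × φ/(1−Φ) = −10 + 12r × 0.945

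For ρ = −0.3, r = −0.134 and 12r = −1.61. The effects are −10 + 1.06 = −8.9 and −10 − 1.52 = −11.5.

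| ρ | <1250 mg | ≥1250 mg | Spurious difference (upper − lower) |
|---|---|---|---|
| 0 | −10.0 | −10.0 | 0 |
| −0.073 | −9.7 | −10.4 | −0.6 |
| −0.3 | −8.9 | −11.5 | −2.6 |
| −0.5 | −8.2 | −12.5 | −4.3 |
| +0.3 | −11.1 | −8.5 | +2.6 |

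Simulation with 1,000,000 per arm agrees to about 0.1 point. With a titration SD of 100 to 300 mg, the difference at ρ = −0.3 runs from −1.4 to −3.5.

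**4. Trial size.** With 27 per arm split equally, each of the four cells holds 13.5, and the interaction SE is 12 × √(4/13.5) = 6.5 points. In 10,000 simulated trials (2×2 interaction t-test, no country or baseline covariate), the 5% test rejected in about 5% at ρ = 0 and −0.073, 6% at −0.3 and 10% at −0.5. Other assumptions (baseline SD 500 mg, titration SD 250 or 500 mg, some with a prognostic baseline dose) gave 9% to 22% for |ρ| of 0.3 to 0.5. With the baseline dose in both arms, rejection stayed at about 5% throughout and both strata stayed at −10.

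**5. Bias without response-tracking.** Now let baseline dose correlate 0.3 with outcome, let titration noise be unrelated to outcome, and let LCIG doses rise by 250 mg on average.

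- OMT: c = 100/400 = 0.25, and the stratum means move by −2.3 and +3.5.
- LCIG: c = (1250 − 1400)/447 = −0.335 and 12r = 12 × 0.3 × 400/447 = 3.22, so the stratum means move by −3.3 and +1.9.
- Effects: −10 + (−3.3 + 2.3) = −11.0 and −10 + (1.9 − 3.5) ≈ −11.5.

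A 500 mg rise gives −12.3 and −12.4. The interaction is small in both cases, but both stratum effects are wrong.

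**6. What the documents say about ρ.** Protocol 3.0 reports: "An increase in levodopa-carbidopa intestinal gel dose was not significantly correlated with increased" ON time with troublesome dyskinesia, with r = −0.073 (double-blind) and −0.001 (open-label). These are post hoc and concern diary time, not UDysRS. With 11 LCIG patients in the double-blind subgroup, the approximate 95% interval for −0.073 is −0.64 to +0.55. With 144 in the open-label study, it is about ±0.16 around zero.

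**The case against.** The strongest counter-argument concerns consequence. This is one of five supportive subgroup factors outside the gatekeeping sequence, and SAP 9.6 ties no decision to the interaction P value. At the correlations the protocol reports, the spurious difference is at most about 0.6 points under the main assumptions, roughly a tenth of the 6.5-point SE. The starting LCIG dose is derived from prior oral levodopa (Protocol 5.5.1.2), which anchors the titrated dose to a pre-treatment value. The OMT diary dose should be close to baseline, so the problem lies mainly in the LCIG arm. All of this stands, and it limits how serious the point is.

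It is also true that a correlation between titrated dose and outcome does not by itself create bias. A dose equally prognostic in both arms and unchanged by titration leaves both strata at −10. Bias needs a titration change, related to outcome or acting on a prognostic baseline dose. That condition is plausible here because the dose is individually titrated. Even an uncorrelated change with SD 200 mg on a baseline dose of prognostic correlation 0.3 gives −9.8 and −10.4.

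Finally, the SAP may intend to study the dose actually reached on LCIG. That is a legitimate question, but it has no counterpart in the OMT arm, so a treatment contrast within dose strata cannot answer it.

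**Conclusion.** The concern holds. The levodopa subgroup is defined after randomisation, by different rules in the two arms, and enters a treatment-by-subgroup model, while a baseline dose is already defined in the same SAP. The analysis as written cannot reliably show whether the LCIG effect depends on levodopa dose.

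Direction and size are unknown. Under the main assumptions the spurious difference is 0.6 points at a correlation of 0.073, 2.6 at 0.3 and 4.3 at 0.5, with the sign following that of the correlation. The dose distribution, the titration spread and the correlation are all assumed, so these figures illustrate the mechanism and do not estimate the bias. The primary analysis and the tested sequence are not affected. The change should be made because it is cheap, not because a main conclusion depends on it.

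**What to change.** In SAP 9.6, define this subgroup in both arms by the SAP 8.4 baseline total daily levodopa dose on the day of randomisation, keeping the prespecified 1250 mg cut. Report the titrated dose descriptively within the LCIG arm, with no treatment contrast.

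The cost is one line of text. It also gives a stratum to LCIG patients who stop before their pump settings stabilise. The drawbacks are small:

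- The baseline dose is a single-day value and no Subject Dosing Diary is marked at V3. However, anti-PD regimens must be stable for 30 days before V3, and dose and frequency are recorded as concomitant medication.
- The documents do not show whether 1250 mg splits baseline doses evenly.
- The interaction remains imprecise under either definition (SE about 6.5 points).

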10.0 Safety Analysis

10.1 General Considerations

Unless noted otherwise, all safety analyses will be performed on the Safety Dataset. Treatment group differences in safety parameters are evaluated using two-sided test at the significance of 0.050.

Unless otherwise specified, treatment group differences in continuous safety variables (e.g., changes from baseline to final observation on laboratory test variables) will be assessed using an ANOVA model with the term of treatment, and the treatment group differences in binary safety variables will be evaluated using a Fisher's exact test.

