Unless otherwise specified, the treatment group differences in continuous safety variables (e.g., change from baseline to final observation on laboratory tests) will be assessed using an ANOVA model with the term of treatment, and the treatment group differences in binary safety variables will be evaluated using Fisher's exact test.

8.1.4.1 **OMT and LCIG Treatment Exposure**

The duration of OMT exposure will be calculated for each subject as the date of the last visit minus the date of randomization. The duration of LCIG study drug exposure will be calculated for each subject as the date of the last dose of LCIG study drug minus the date of the first dose of LCIG study drug plus 1. The duration of LCIG device exposure will be calculated for each subject as the date of the last study tube exposure minus the date of the first study tube placement procedure plus 1. For subjects with all study tubes removed on or after the last day of LCIG study drug infusion, the date of last study tube exposure will be the last tube removal date. For all other subjects randomized to LCIG treatment, the date of last study tube exposure will be the day of the final visit. The duration of OMT and LCIG study drug exposure and LCIG device exposure will be summarized with descriptive statistics (number of subjects with non-missing data, mean, and standard deviation, median, minimum and maximum).

8.1.4.2 **Adverse Events**

Adverse events will be coded using the most current version of the Medical Dictionary for Regulatory Activities (MedDRA). Adverse events will be summarized by primary MedDRA system organ class (SOC) and preferred term (PT). Subjects reporting more

than one adverse event for a given MedDRA PT will be counted only once for that term. Subjects reporting more than one adverse event within an SOC will be counted only once for the SOC total. Subjects reporting more than one adverse event will be counted only once in the overall adverse event total.

Each adverse event will be categorized by severity (mild, moderate, severe) and by relationship to study treatment (reasonable possibility, or no reasonable possibility). Detailed search criteria for adverse events of special interest (AESIs) will be defined in an SAP prior to database lock.

A treatment-emergent adverse event (TEAE) is defined as any adverse event with onset during the treatment period or within 30 days of the end of the treatment period:

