4.3 Sample Size

Approximately 60 subjects will be enrolled into the study and randomized in a 1:1 ratio to either optimized medical treatment (OMT) or LCIG treatment. Subject randomization will be stratified by country. For sample size determination, it is assumed that the difference of improvement is 10 points on UDysRS total score between the LCIG treatment group and OMT group based on results reported by Pahwa et al (2015). The pooled standard deviation is assumed to be 12 based on results reported by Goetz et al (2013). Assuming that the treatment group difference is 10 points and the pooled standard deviation is 12, 27 subjects per group will have 85% power to declare statistical significance on the primary endpoint at a two-sided significance level of 0.050 based on calculations using nQuery + nTerim 4.0. It is further assumed that 10% of randomized subjects in either treatment group will not provide post-randomization efficacy assessment. Therefore the total planned enrollment is decided to be approximately 60 subjects.

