6.2 Definition of Study Epochs and LCIG Treatment Period Reference Variables

The following study epochs have been defined to track each subject's progression from screening through study completion or premature discontinuation.

Epoch Name	Epoch Description
Pre	
Device Before (LCIG group only)	
Open	
Transition (LCIG group only)	
Device After (LCIG group only)	
Off	

For subjects in the LCIG group, the date and time of the earliest LCIG tube placement (NJ or PEG-J) recorded on the Device Information eCRF will be considered the treatment start reference date (REFDT) and time (DMREFTM). The date of the last LCIG tube removal, or the date of the last LCIG infusion if there is no device removal will be considered the end of the LCIG treatment period and the following day will be the post-treatment start reference date (REFEDT). For subjects in the OMT group, the date after randomization will be considered the start of treatment period and will be the treatment start reference date (REFDT). The date of the final visit will be considered the end of the OMT treatment period and the following day will be the post-treatment start reference date (REFEDT).

Study Days will be calculated based on the treatment start reference date (REFDT). For time points before REFDT, the Study Day = time point - REFDT. For time points on or after REFDT, the Study Day = time point - REFDT + 1. Thus, the Study Day is a negative value when the time point of interest is prior to REFDT and the Study Day is a positive value when the time point of interest is on or after REFDT. There is no Study Day 0. The Study Day will be labeled as Rx Day on the data listings. RxEnd Day is calculated for each post-treatment time point as the number of days between REFEDT and the specific time point: RxEnd Day = date of time point - REFEDT + 1.

6.3 **Definition of Baseline and Final Observation**

Baseline for PD Diary variables will be the average of the last 3 valid diaries completed on or before the day of randomization. Baseline for all efficacy, health outcome and safety measures, other than the PD Diary, will be defined as the last non-missing observation that is on or before the day of randomization.

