9.3 Additional Efficacy Analyses

Secondary Analysis of the Primary Efficacy Variables

Analysis of covariance (ANCOVA) analyses will be carried out on change from baseline to final UDysRS total score. The ANCOVA model will contain treatment and country as the main effects and baseline score as the covariate. Sensitivity analyses will be carried out on the above variables with the same ANCOVA model using all randomized subjects. In this analysis, Baseline Observation Carried Forward (BOCF) will be applied to subjects who do not have post-randomization assessment of UDysRS.

Analysis of Secondary Efficacy Variables

The MMRM model and the descriptive statistic summary described for the UDysRS total score will also be used to evaluate the change from baseline to Week 12 in each of the following efficacy endpoints (with the exception of the CGI-C, which the score itself shows the changes):

- "ON" time without troublesome dyskinesia as measured by the PD Diary
- Parkinson's Disease Questionaire-8 (PDQ-8) summary index
- Clinical Global Impression of Change (CGI-C) Score
- UPDRS Part II Score
- "OFF" time as measured by the PD Diary
- **UPDRS** Part III Score

PD Diary variables will be normalized to a 16 hour awake time and the time recorded by the subject on the 3 diaries completed prior to each visit will be averaged.

For CGI-C, an ANCOVA model containing treatment and country as the main effects and baseline CGI-S as covariate will be carried out.

"ON" time without troublesome dyskinesia as measured by the PD Diary, PDQ-8 summary index, CGI-C score, UPDRS Part II and Part III score, and "OFF" time as measured by the PD Diary are key secondary endpoints. If the primary efficacy variable is statistically significant, each of the secondary variables will be tested using the fixed sequence above as a gatekeeping procedure and at α level of 0.050. Testing will cease at the point that a secondary variable fails to demonstrate statistical significance.

All secondary efficacy variables will be summarized by the number of subjects with nonmissing data, mean, standard deviation, median, minimum and maximum.

Analysis of Additional Efficacy and Health Variables

Efficacy will also be assessed using the following additional measures:

- UDysRS Historical Score, Objective Score and Parts 1 through 4 Scores
- "ON" time with troublesome dyskinesia and "ON" time without dyskinesia as measured by the PD Diary
- mAIMS

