10.3.1 Analysis of Mean Changes for Laboratory Tests

Analyses of mean change from baseline to each planned visit and to the minimum, maximum and final value during the 12-week Treatment Period will be presented by treatment group for each continuous hematology, chemistry, urinalysis, and special laboratory variable.

For each change from baseline analysis, the following summary statistics for each treatment group will be presented: sample size, baseline mean, visit mean, and the mean, standard deviation, and median of the change from baseline. The baseline and visit means will be calculated for each visit for subjects who have both a baseline and visit value. The mean changes for the LCIG group and for the OMT group will be compared using an ANOVA with treatment as the factor. LS mean, standard error, 95% confidence interval and *P* value will be presented.

[figure not shown]
Analyses of mean change from baseline to each planned visit and to the minimum, maximum and final value during the Transition Period will be presented for each continuous special laboratory variable for LCIG subjects who enter the Transition Period.

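### Between-arm tests of change in laboratory, vital-sign, weight and ECG values leave out the baseline value; adding it protects against chance imbalance and narrows most intervals, with weight and BMI essentially unchanged

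*SAP*

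**What the plan says.** SAP 10.1 sets the default for continuous safety variables: differences "will be assessed using an ANOVA model with the term of treatment". It makes this formal inference: "Treatment group differences in safety parameters are evaluated using two-sided test at the significance of 0.050". Protocol 8.1.4 has the same rule, with differences "assessed using an ANOVA model with the term of treatment".

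SAP 10.3.1 applies the rule to laboratory variables: "The mean changes for the LCIG group and for the OMT group will be compared using an ANOVA with treatment as the factor". Sections 10.4.1 (vital signs and weight) and 10.5.1 (ECG) do likewise. All three ask for LS means, standard errors, 95% CIs and P values. None of these models contains baseline or country.

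The baseline value is already defined in SAP 6.3: it "will be defined as the last non-missing observation that is on or before the day of randomization". The baseline and visit means in each change analysis are calculated "for subjects who have both a baseline and visit value".

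For efficacy the plan does adjust. In SAP 9.3, "The ANCOVA model will contain treatment and country as the main effects and baseline score as the covariate". The MMRM in 9.2 and the subgroup ANCOVA in 9.6 also carry baseline, and the CGI-C model uses baseline CGI-S. The documents give no reason for treating safety differently.

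**The concern.** Subtracting baseline is not the same as adjusting for it. With equal SDs at both times and r below 1, a change score is negatively correlated with its own baseline. An arm that happens to start high is expected to fall more, treatment aside. In an ANOVA of change, a chance baseline difference of D therefore moves the estimated treatment difference by an expected −(1 − r)D. The model also leaves in the residual the part of the variation that baseline could explain, so its interval is wider than it needs to be when r is modest.

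These comparisons bear on known risks. Polyneuropathy and weight loss are adverse events of special interest (Protocol 6.2.3), and orthostatic hypotension is an important identified risk (Protocol 3.2). The earlier open-label data in Protocol Table 2 show decreased vitamin B6 in 15.8%, increased homocysteine in 13.6% and orthostatic hypotension in 10.7%. With about 60 subjects, chance baseline gaps matter. The SAP also rules out group comparisons for the PCS values (10.3.3, 10.4.3, 10.5.2) and BMI shifts (10.4.2), so the mean-change model is the main planned between-arm test of these measurements.

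**Working it through.** **The plan's own figure.** SAP 4.3 assumes that "the treatment group difference is 10 points and the pooled standard deviation is 12", at two-sided 0.050. The noncentral t calculation gives 83.8% power with 26 per group and 85.2% with 27, so the stated 27 per group and 85% reproduce. With 10% loss, 27/0.9 = 30 per group, or 60 in total. The SAP gives no figure for the safety comparisons. I use 27 per arm (N = 54) below; the safety dataset could hold up to about 30 per arm.

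**Assumed input.** The correlation r between baseline and follow-up is not in the documents. The values below are an assumed range, with equal SD s at both times.

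**Precision.**
- Variance of change: 2s²(1 − r). Residual variance with baseline in the model: s²(1 − r²). Ratio: (1 + r)/2.
- Estimating the slope multiplies this by 1 + 1/(N − 4) = 1 + 1/50 = 1.02.
- The t quantile moves from 2.0066 (52 df) to 2.0076 (51 df), a factor of 1.0005.
- CI width ratio = √[1.02 × (1 + r)/2] × 1.0005.

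| r (assumed) | 1.02 × (1 + r)/2 | CI width ratio | Effect of adding baseline |
|---|---|---|---|
| 0.5 | 0.765 | 0.875 | 12.5% narrower |
| 0.7 | 0.867 | 0.932 | 6.8% narrower |
| 0.8 | 0.918 | 0.959 | 4.1% narrower |
| 0.9 | 0.969 | 0.985 | 1.5% narrower |
| 0.98 | 1.010 | 1.005 | 0.5% wider |
| 0.99 | 1.015 | 1.008 | 0.8% wider |

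Break-even is at r = 0.959 (0.963 at N = 60). Weight is likely above it. For illustration, assuming a between-subject SD of 15 kg and a change SD of 3 kg, r = 1 − 9/(2 × 225) = 0.98.

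A simulation with 27 per arm and 40,000 runs per r gave the same width ratios to within 0.001. Where the ANOVA has 80% power, it gave ANCOVA about 89% at r = 0.5, 85% at 0.7, 81% at 0.9 and 79.5% at 0.99.

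**Error given a baseline gap.** For a chance gap of k standard errors and no treatment effect, the ANOVA statistic is approximately normal with mean k√[(1 − r)/2] and variance (1 + r)/2.
- r = 0.5, k = 2: mean 1.000, SD 0.866. The upper tail beyond (1.96 − 1.000)/0.866 = 1.109 is 13.4%; the lower tail is 0.03%. Total 13.4%.
- r = 0.7, k = 2: mean 0.775, SD 0.922. Tails 9.9% and 0.15%. Total 10.1%.
- k = 1.5: 8.2% (r = 0.5) and 7.0% (r = 0.7).
- k = 1: 4.8% and 4.9%.
- k = 0 (balanced arms): 2.4% and 3.4%.

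**Simulation check.** Overall type I error was about 5% with either model at every r. A baseline gap above 0.4 SD is 0.4/√(2/27) = 0.4/0.272 = 1.47 standard errors, and it arises by chance in about 14% of variables. Among those runs the ANOVA's error was 12.5% (r = 0.5), 9.4% (r = 0.7) and 6.2% (r = 0.9). With baseline in the model it was 4.4%, 5.1% and 4.7%.

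**The case against.** A treatment-only ANOVA of change is a valid randomization-based comparison. The raised conditional error at large gaps is offset by error below 5% for gaps under about 1 standard error, which covers nearly 70% of variables. A reader might infer from the 13% figure that the planned safety tests have an inflated false-positive rate. They do not; the overall rate is about 5%.

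A reader might also infer that baseline adjustment tightens every interval at no cost. That does not hold above r of about 0.96, and weight loss is a special-interest event. The documents give no r for any variable, so nothing shows which row of the table applies to vitamin B6, homocysteine, blood pressure or QTc. The width formula is also not derived for changes to the minimum or maximum, because extremes over visits need not share the baseline variance.

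Finally, these are supportive tests with no stated multiplicity control. The safety picture also rests on adverse-event searches, PCS counts that require a value more extreme than baseline, and shift tables. Baseline means by arm will be shown, so an imbalance would be visible.

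All of this stands as a limit on size and importance. It does not remove the point. Seeing an imbalance is not correcting for it, and the reported differences, CIs and P values would still carry it.

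**Conclusion.** The point holds as an improvement to a valid analysis, not as an error in it. Adding baseline keeps the error near 5% whatever the chance imbalance. For an assumed r of 0.5 to 0.9 it narrows the interval by about 12.5% down to 1.5%. Above r of about 0.96 it costs at most about 0.8% of CI width over the values examined (r up to 0.99), so it is essentially neutral for weight and BMI.

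These figures rest on the assumed r, equal SDs at the two times and 27 per arm, and they apply to change to a visit or to the final value. The primary conclusion and the sample size are unaffected. The change is worth making before database lock.

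**What to change.** In SAP 10.1, 10.3.1, 10.4.1 and 10.5.1, replace the ANOVA with an ANCOVA that has treatment as the factor and the variable's own baseline value as covariate. Report the adjusted LCIG minus OMT difference with its 95% CI.

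SAP 12.0 now states that the analysis is unchanged from Protocol Amendment 1. Replace that statement with an entry recording this departure from Protocol 8.1.4 and the reason for it. The protocol rule applies unless otherwise specified, so the SAP can specify the model, but the entry is needed to keep the two documents consistent.

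The cost is one degree of freedom per model, a negligible loss of precision for very highly correlated variables, one added model term in the programs, and the documentation entry. No new data are needed. No subject is lost, because every change score already requires a baseline value.
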